MDS Minimum Data Set QC Quality Control

SADE Serious Adverse Device Effect

SAE Serious adverse event

SOC Standard of care

STEADI Stopping Elderly Accidents, Deaths, & Injuries

POA Person Of Authority

UADE Unanticipated Adverse Device Effect

Protocol Synopsis

Reference ID/Protocol Number: COP-0001

Title: Mitigation of Major Hip Injury due to fall in an At-Risk, Older Adult Population with a

Wearable Smart belt

Sponsor: Active Protective Technologies, Inc

Regulatory Status: Non-significant risk pivotal study of medical device

Objectives: Primary Objective: To assess the performance of the Tango® Belt to mitigate fall-related

major hip injuries in an at-risk of fall adult population as compared to the standard of

care (SOC) only.

Secondary Objectives: To assess the performance of the Tango Belt to mitigate falls resulting in: (1) hip fractures, (2) emergency department visits or (3) hospitalizations.

Study Design: Multi-center, comparative, non-significant risk adaptive study with retrospective

controls.

After providing informed consent and being screened for eligibility, intervention subjects will be prescribed and provided an appropriately sized Tango Belt. The subject must demonstrate a minimum of 64% adherence to the use of the Tango Belt within 14 days of initiation to fully enroll in the study. Upon demonstration of at least minimum adherence, the subject will be provided the Tango Belt to wear continuously for at least 6 months, except during bathing, device charging, and as deemed by clinical staff.

The study will investigate the safety and effectiveness of the Tango Belt with the primary and secondary endpoints being taken every 3 months and at the end of the study run time from the electronic medical record. Additionally, ancillary endpoints on

adverse events and device performance will be gathered.

Study Population: Subjects must be older adults (≥65 years of age) who are at risk for fall with

major hip-related injury as determined by the SOC for fall-risk management.

Number of Patients: Estimated up to 417 in the treatment group and up to 1688 in the control group.

Final sample size to be determined from retrospective control data.

Study Duration: Estimated enrollment time 3 months

Estimated in-study run time 6 months

Estimated total duration 12 months after 1st subject enrolled

Eligibility Criteria

Inclusion Criteria (ALL of the following criteria):

- 1. Age 65 years or older;
- 2. Have experienced a fall-related fracture after age 50
 - Have experienced one or more falls in the 12-months prior to consent and have a diagnosis of osteoporosis, osteopenia, or prescribed osteoporosis medication.
- 3. Independently or with staff or caregiver assistance, able to transfer between surfaces (e.g., to or from a bed, chair, wheelchair, toilet, standing position) or walk or move between locations (use of an assistive device such as a walker is acceptable);
- 4. Have a waist circumference between 29 50 inches (63.5 127 cm);
- 5. Able to comply with required study procedures and follow-up schedule as determined by the Study Investigator;
- 6. Are under the care of the Investigational organization;
- 7. Provides consent or their legally authorized representative provides consent on subject's behalf

Exclusion Criteria (ANY of the following criteria):

- 1. Age 64 years or less;
- 2. Participation in a different clinical investigation that can conflict with this clinical study as determined by the Study Investigator and approved by the Sponsor;
- 3. Total dependence on staff or caregiver assistance to be able to transfer between surfaces (e.g. to or from a bed, chair, wheelchair, toilet, standing position) and walk and move between locations:
- 4. Use of other devices or interventions outside of SOC for fall risk management during study participation without Sponsor approval;
- 5. Unable to comply with required study procedures and follow-up schedule as determined by the Study Investigator;
- 6. Does not provide consent, or legally authorized representative does not provide consent

Investigational Device Tango® Belt

Route of Administration The Tango Belt is a device intended to be worn around the waist and is designed to:

- Recognize serious hip-impacting falls in progress
- Deploy an airbag upon detection of a serious hip-impacting fall in progress to protect the hip region from potential major injury
- Communicate fall and impact alerts to designated persons

Schedule of Visits The study is composed of the following study intervals:

Baseline Enrollment, screening, and provision of Tango Belt

14-day Run-in for adherence screening90-days EMR screening for endpoints

180-days EMR screening for endpoints and completion of participation

Table of Contents

Title Page 1					
List of Abbreviations and Definition of Terms 2					
Protocol Summary/Protocol Synopsis 3					
1.	Key Roles				
	1.1	Key roles listed	8		

	18.2. Study Questionnaires					
	18.3.	Literary	y References	56		

Version Information

Revision	Date	Description
1.0	28 Jan 2022	Original Protocol
2.0	18Apr2022	Protocol with simplification of adjudication process noted in sections 7.3 and 8.3 iii

1. Key Roles

2.1 Background information

Every year in the United States there are approximately 3 million fall-related emergency room visits for geriatric adults. Of the 3 million emergency room visits, approximately 300,000 of those lead to hospital admissions due to hip fracturesⁱ. This coincides with the Centers for Disease Control (CDC) analysis that 1 out of 4 adults over the age of 65 (i.e., geriatric) will fall each year and those falls may occur more than once in a yearⁱⁱ. As a result of these high numbers, falls are the leading cause of injury-related deaths among the geriatric US population and cost over \$50 billion in total medical costsⁱⁱⁱ.

The standard of care (SOC) in the US for managing the fall risk of geriatric patients is the CDC's Stopping Elderly Accidents, Deaths, and Injuries (STEADI) initiative, which implements the America and British Geriatric Societies" Clinical Practice Guidelines for fall risk management. The STEADI algorithm consists of tools and resources for healthcare providers for fall risk screening, assessment, and intervention iv,v. Screening and assessment includes identifying fall history and modifiable factors related to fall and fall injury risk (e.g. fear of falling, gait, strength, balance, medications, comorbidities, etc.); then interventions to reduce the fall and fall injury risk are applied based upon assessment findings, and can include physical therapy, medication adjustments, patient education, bed and chair alarms, bed rails, etc. vi Healthcare providers have also used passive hip protectors as an intervention to mitigate hip fracture for those identified with a fall risk. It has been shown that passive hip protectors are able to reduce hip fractures by over 80% when worn during the fall vi, viii. However, the clinical utility of passive hip protectors has been questioned, as compliance of wearing the hip protectors has proven to be low due to a variety of factors, most commonly related to comfort and difficulty taking them on and off.ix,x

Despite the broad adoption and utilization of the STEADI algorithm as the SOC for fall risk management, the number of older adults experiencing falls and fall related injuries has increased or remained unchanged since 2012^{xi} . Furthermore, per the CDC, fall death rates in the U.S. have increased 30% from 2007 to 2026 among older adults. Lastly, multiple large clinical trials have recently shown that the aforementioned SOC for fall risk management was ultimately unsuccessful in reducing the rate of falls with injury. $^{xii, \, xiii}$ As such, there is a significant unmet need for new interventions for geriatric individuals who are at high risk of fall, as the existing SOC is not effective at reducing the overall rate of fall injuries.

2.2 Scientific Rationale

As a solution to the need for fall injury mitigation, Active Protective Technologies, Inc. ("APT") has developed the Tango® Belt, a wearable device primarily designed to protect geriatric individuals against major hip injuries due to a serious hip-impacting fall. Hip injuries are considered major if they are life-threatening, result in hospitalization or

emergency care, require medical intervention, or result in disability or permanent damage. A fall that results in major hip injury is described herein as a serious hipimpacting fall. The Tango Belt uses motion sensors and proprietary algorithms to determine if the wearer is experiencing a serious hip-impacting fall in progress and automatically deploys an automotive-grade cold-gas airbag around the hips to attenuate ground impact forces on the body. A longitudinal observational study by Yang et. al. analyzed recordings from thousands of real-world falls captured on closed-circuit video monitoring within the nursing home setting and determined that the vast majority of major hip injuries resulted from falls from standing height and ground-force impact to the lateral or posterolateral aspect of the hip. xiv Lastly, as referenced above, a randomized clinical trial of over 1200 subjects within nursing homes demonstrated that passive hip pads were able to reduce the incidence of hip fracture by over 80% when worn during the fall. These studies provide an evidence-based approach to mitigating fall-related major hip injuries via attenuation of ground impact forces and utilizing a belt-based form factor specifically designed to overcome common barriers to wear compliance.

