2.4 Demonstration of the Safety and Effectiveness of study product

Laboratory performance testing of the serious hip-impacting fall-in-progress detection algorithm was conducted using APT's staged true-fall library and demonstrated sensitivity of 82%. This testing includes inertial data sensor recording, prototype sensor and airbag-disabled belt assemblies, and pre-production sensor and airbag-disables belt assemblies. Further, with respect to specificity, there were 10 false positives (i.e., false alarms) over 66,000 wear-hours. Laboratory testing includes extensive design verification testing to confirm safety and functionality of the hardware and software, including impact attenuation on crash test dummies, environment conditioning, out-of-position deployment, FCC certification, electromagnetic emissions and immunity, belt and companion app usability, etc. In conjunction with the real-world evidence noted above, testing performed to date has demonstrated that the Tango Belt is safe and performs as intended.

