2.5 Potential Known Risks and Benefits

Risks to subjects in this study include, but are not limited to, the following: use error or ineffective intervention leading to impact-related injury, adverse tissue reactions and interference with other electrical equipment/devices.

Presently, there are no known adverse events associated with the Tango Belt itself that have arisen throughout the pre-clinical testing and real-world usage.

Potential benefits of the Tango Belt include mitigating major hip injuries due to falls and reducing emergency department visits and hospitalizations due to falls, thereby enabling safer mobility in older adults at risk of falls and fall injuries.

3. Purpose/Intended Use

Purpose:

The current comparative clinical study is intended to establish the safety and effectiveness of the Tango Belt as an adjunctive intervention to the standard-of-care (SOC) to mitigate major hip injuries due to falls in an older adult population at-risk for fall injury.

Intended Use:

The Tango Belt is intended to be worn around the waist by geriatric individuals (65+ years of age) at risk for fall injury in order to mitigate major hip injuries related to falls. The Tango Belt uses built-in sensors and algorithms to detect falls and impacts. The device can send an alert to the designated caregiver/healthcare providers upon detection of a fall or impact. When an inprogress serious hip-impacting fall is detected, an airbag will deploy to physically protect the hip region from potential major injury. The Tango Belt is for prescription use only.

4. Study Design, Duration, Objectives and Endpoints

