6.1 Device

The Tango Belt (the "Device") is a wearable belt designed to enable safer mobility of geriatric individuals (≥ 65 years of age) at risk for fall injury by mitigating major hip injuries due to falls. The Tango Belt is a patient-contacting electronic device made out of medical grade plastics and biocompatible fabrics. It is worn around the waist at the iliac crest, secured by a buckle. It comes in 5 sizes, XS, S, M, L, and XL, to accommodate wearers with a waist circumference between 29-50 inches (covering the 5th-95th percentile of older adults in the US); each belt is further adjustable to prevent sliding past the hips or elevating out of position.

The Tango Belt contains a fall-in-progress detection algorithm which can detect a serious hip-impacting fall-in-progress using built-in sensors and deploy an automotive-grade cold-gas airbag to protect the hips from ground impact forces. When connected to Wi-Fi, the Tango Belt can send automated fall and impact alerts to caregivers and Healthcare Providers (HCPs) while recording motion and event data, which can then be analyzed for usage-based metrics viewable via a companion mobile app and/or desktop app. The Tango Belt can also send manually activated alerts for help, triggered by pressing a button on the belt buckle, when connected to Wi-Fi. Alerts are sent in the form of SMS texts and emails to alert recipients designated in the mobile or desktop Companion App. The Tango Belt can also detect non-serious hip-impacting or non-hip impacting falls in which the wearer may have incurred a minor injury (i.e., not a major hip injury) and/or may be unable to get up.

Additionally, the belt can be periodically surface disinfected using a germicidal wipe. Further, the belt contains a non-replaceable lithium-ion battery, which requires recharging via the included specially designed AC adapter every several days depending on wear duration. An optional Safety Latch can be installed by care staff on any belt to prevent inadvertent unbuckling. Lastly, if airbag deployment occurs, the Tango Belt cannot be reused.

The Tango Belt's Companion App (available in mobile and desktop versions) enables the following added functionality: 1) connecting the belt to Wi-Fi (mobile version only), 2) inputting contact information for alert recipients, 3) viewing dashboard metrics (e.g. Compliance and Daily Wear), 4) taking or administering the FES-I survey, and 5) managing a fleet of multiple belts within a facility setting.

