 Metrics of the compliance to wear of the Tango Belt by the subject defined as at minimum 64% (at least 1 hour a day for 9 days out of 14) will be provided by sponsor to the CRA. If the subject is not utilizing the device for at least the minimum amount of time, they will be determined to be a screen failure and withdrawn.

Visit 3 Midterm (90 days +/- 10):

- Metrics of changes in fall mitigation plan, mobility level and fall events including falls, falls with major injury, adverse events (whether not pertaining to the Tango Belt), emergency department visits, and hospital admissions will be taken by the site investigator or designee research assistant directly from the MDS and/or EMR within the electronic documentation system utilized at the clinical study site.
- Metrics of Tango belt wear days and wear hours/day will be provided to the site investigator or designee research assistant from the sponsor or obtained from the Tango Belt Companion App.
- Metrics of device deficiencies, device discrimination between types of falls, airbag deployments, and alerting will be provided to the site investigator or designee research assistant by sponsor from the Tango Belt cloud.

End of Study (180 days +/- 30):

 Metrics of changes in fall mitigation plan, mobility level and fall events including falls, falls with major injury, adverse events (whether or not pertaining to the Tango Belt), emergency department visits, and hospital admissions will be taken by the site -

- investigator or designee research assistant directly from the MDS and/or EMR within the electronic documentation system utilized at the clinical study site.
- Metrics of Tango belt wear days and wear hours/day will be provided to the site investigator or designee research assistant by sponsor or obtained from the Tango Belt Companion App.
- Metrics of device deficiencies, device discrimination between types of falls, airbag deployments, and alerting will be provided to the site investigator or designee research assistant by sponsor from the Tango Belt cloud.
- Tango Belt will be collected by the sponsor for return to Active Protective Technologies, Inc.

Unscheduled Visit (AE, hospitalization, change in status in medical care plan):

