Apparent Device malfunctions can be troubleshooted by site staff following provided materials, or by contacting sponsor for support, and should be recorded in patient files, along with initial date of occurrence, brief description, did it cause adverse events, whether damage is apparent. Malfunctions that impact essential performance, as defined in the Instructions for Use, should be recorded immediately and reported immediately to site-investigator. The site investigator may seek additional support from sponsor, but records in the EDC when a device is replaced due to malfunction, with date of replacement and start of malfunction. A device that doesn't maintain essential performance, as defined in the Instructions for Use, should be replaced (e.g. fails to power on, deploys without a fall, solid red light, blinking blue light). The site shall coordinate with the Sponsor Monitor for return and replacement, as needed.

All adverse events are to be evaluated for severity, relationship to product and whether they constitute an SAE, recorded in the EDC, to be reviewed by PI as described in section 8.4. PI continually monitors the enrolled study subjects for AEs and possible SAEs in the medical record.

PI should be notified immediately upon, Serious Adverse Event, fall event, or an AE that impacts utilization of the device.

Serious Adverse Events (SAE's) including status changes indicated in study subject medical records receive immediate attention of the Principal Investigator (PI) for consideration of device-related SAE. Serious AE (SAE) are to be reported to Sponsor and the IRB within 24 hours of the site becoming aware of the event. SAE notifications to the Sponsor are to be reported and completed via EDC.

Upon a fall event, site investigator is to initiate a Fall report, to gather evidence needed for the eventual adjudication of the Adverse Event, if required. Falls with Major Injury will be reviewed by the medical expert adjudicator as outlined in section 7.3. (Note, a Fall with Major Injury could *also* be considered a SAE for purposes of IRB reporting).

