To estimate performance of the Tango Belt, data on file from real-world use of the Tango Belt in the nursing home setting found airbag deployment in 6 of 6 total serious hip-impacting falls, resulting in no major hip injuries. Therefore, we are 95% confident that the Tango Belt will protect 66% of falls. However, it is possible that the Tango Belt may prove to be even more effective with a larger sample size. Therefore, a group sequential design (GSD) will be utilized. The GSD will include a planned interim analysis at a sample size to detect an 80% protective effect of the Tango belt at 80% power at a planned interim analysis. If a significant difference is found between the prospective Tango Belt subjects and historical controls at the interim analysis, the study will be completed early. If not, enrollment will continue until a final sample size is reached to detect a 60% protective effect of the Tango belt at 80% power and a 5% total level of significance. Exact sample sizes for the interim and final analysis will be calculated once the number of historical control subjects and the rate of falls with major hip injury in the control group are determined. The PASS GSD module will be used to simulate the sample sizes and power using the Pocock alpha-spending function. The steps to calculate the sample size will include:

- 1. Test the historical control time periods to determine if all the time periods can be used, depending on if any time periods differ in fall rate
- 2. From the remaining historical control data, find the fall rate and the total sample size available for the historical control group
- 3. Find the sample sizes for the historical controls and the prospective Tango Belt arm at the interim analysis.
- 4. Find the sample size for the prospective Tango Belt arm at the final analysis; the total sample of historical controls will be used at this look.

To demonstrate these calculations, we assumed subjects were followed for an average of 6 months, an annual fall-with-major-hip-injury rate of 8%, and sufficient historical control subjects to allow 1:4 allocation of subjects to treatment and control. This would require 176 subjects in the prospective Tango belt group and 704 subjects in the historical control group at the interim analysis. At the end of the study (should the

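### A serious hip-impacting fall is defined by the injury it causes, and fall type is otherwise labelled only by the belt's own cloud, so the ancillary device-discrimination endpoint cannot be estimated as written

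*Combined protocol and SAP*

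**What the plan says.** **Definition by outcome.** Protocol 2.2 first says when a hip injury counts as major, then adds: "A fall that results in major hip injury is described herein as a serious hipimpacting fall". Section 6.1 treats the opposite class in a similar way: "The Tango Belt can also detect non-serious hip-impacting or non-hip impacting falls in which the wearer may have incurred a minor injury".

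**Use before any outcome.** The synopsis says that the belt is designed to "Deploy an airbag upon detection of a serious hip-impacting fall in progress to protect the hip region from potential major injury". Sections 2.2, 3 and 6.1 likewise speak of a fall in progress that the belt recognises before impact.

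**Use against the definition.** Section 10.1 supports the assumed effect with field data: "airbag deployment in 6 of 6 total serious hip-impacting falls, resulting in no major hip injuries".

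**Endpoint and data source.** Discrimination of serious hip-impacting falls from other falls is an ancillary endpoint (protocol 4.4, SAP 3.2.3). Under protocol 7.3, metrics of "device discrimination between types of falls, airbag deployments, and alerting will be provided to the site investigator" by the sponsor, from the belt cloud. Neither document describes a reference classification of fall type. The SAP gives the endpoint no derivation beyond the general descriptive conventions of its section 6.

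**Related safety text.** Section 2.5 names first among the risks "use error or ineffective intervention leading to impact-related injury". The malfunction examples in 8.3 iii are "fails to power on, deploys without a fall, solid red light, blinking blue light".

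**The concern.** An endpoint on how well a device tells two kinds of event apart needs a true label for each event. That label has to be independent of the device and unaffected by what the device then does. Neither available label qualifies.

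- **The 2.2 label is affected by the treatment.** If the airbag deploys and prevents the injury, the fall no longer meets the definition. The device's success then counts as a deployment in a non-serious fall.
- **The cloud label comes from the device.** The detection that classifies a fall as serious also triggers the airbag. A serious fall that the algorithm missed is stored as another type of fall, or not at all.

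At stake is what the trial can say about device performance: how often a worn belt fired in a fall it was built to catch, and how often it stayed silent. That also bears on the first risk in 2.5.

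**Working it through.** **1. The plan's own figure.** Section 10.1 reports 6 of 6 and reads this as 95% confidence that 66% of falls are protected. The exact lower limit for 6/6 is 0.05^(1/6) = 60.7% one-sided and 0.025^(1/6) = 54.1% two-sided. The nearest variants tried are a uniform-prior one-sided limit (65.2%) and a Jeffreys two-sided limit (67.0%). The method is not stated, so I do not call 66% an error, and nothing below depends on it. The relevant point is the denominator. Under 2.2, six falls without major hip injury are zero serious hip-impacting falls, so the fraction becomes 0/0 and all six deployments fall in the non-serious class.

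**2. Sensitivity under the 2.2 definition.** Inputs:
- Laboratory testing on staged falls "demonstrated sensitivity of 82"% (protocol 2.4). I assume that this carries over to real falls.
- p = probability that a deployment prevents the injury. The documents do not give it, so I use 60%, 80% and 100%.
- Every missed fall injures (assumption).

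Take 100 worn-belt falls that would injure an unprotected hip: 82 deploy and 18 are missed. Only injured cases count as serious, so

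sensitivity = 82(1 − p) / [18 + 82(1 − p)].

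| p | Deployed, injured | Deployed, injury prevented | Missed, injured | Sensitivity under 2.2 |
|---|---|---|---|---|
| 0 | 82 | 0 | 18 | 82% |
| 0.6 | 32.8 | 49.2 | 18 | 32.8/50.8 = 65% |
| 0.8 | 16.4 | 65.6 | 18 | 16.4/34.4 = 48% |
| 1.0 | 0 | 82 | 18 | 0% |

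The true value is 82% in every row. The computed value falls as the airbag works better. If an unprotected fall injures with some common probability q below 1, q cancels from numerator and denominator and the percentages stay the same. However, 18(1 − q) misses then cause no major injury and disappear from the count.

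**3. Sensitivity with the cloud label as reference.** Falls labelled serious are those the algorithm detected as serious, and those are the ones that trigger the airbag. Deployed divided by labelled serious is therefore close to 100% whatever the detection rate. It could show an airbag that failed to inflate after detection, but not a fall that went undetected.

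**4. What the planned data can and cannot show.**
- *Worn belt, no deployment, major hip injury:* countable. Falls come from the MDS/EMR (7.3), injury is adjudicated independently on blinded data (7.3), EDC and cloud data are to be matched (6.6), and SAP 5.2.3 presupposes that wear at the primary event is known.
- *Worn belt, no deployment, hip impact without major injury:* not identifiable.
- *Deployment that prevented an injury:* not separable from deployment in a fall that was never serious.
- *Deployment with no fall:* recordable as a malfunction (8.3 iii).

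**5. Expected number of misses.** SAP section 4 gives 15% as the proportion of control subjects with a major hip injury. SAP 4.1 calls 15% an annual rate with 6 months of follow-up. For 134 intervention subjects, one such fall per affected subject, all with the belt worn:
- 15% over 6 months: 134 × 0.15 × 0.18 = 3.6.
- 15% per year: 134 × 0.075 × 0.18 = 1.8.

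The 134 includes the 30% attrition allowance. On the 94 evaluable subjects the same products are 2.5 and 1.3.

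**The case against.** The strongest case against is that this is loose wording in a background section. No SAP derivation uses the 2.2 sentence, and the operational text uses the term prospectively. Neither document specifies a sensitivity endpoint, and 7.3 says where data come from without making the belt the reference standard. The belt also records non-serious and non-hip falls, so a misclassified fall could appear in the cloud and be compared with the EMR.

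Much of this stands, and it limits the point to ancillary endpoints. It does not remove the point. The endpoint is listed in both documents, the only definition offered is tied to injury, and neither document states the comparison with the EMR or a rule for it.

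A reader might infer more than the documents support:

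- *That failures to deploy cannot be counted at all.* Those that injure can be, by the linkage in step 4.
- *That needless deployments go unrecorded.* Deployment without a fall is a named malfunction in 8.3 iii. Only deployments in real but non-serious falls lack a label. The 2.4 false-alarm rate should not be scaled up to a count for this trial, because it is not stated to be a deployment rate.
- *That the risk named in 2.5 is unmonitored.* The primary endpoint captures the resulting major hip injury, every fall is an adverse event (8.1), and device deficiencies are collected at follow-up (7.2).
- *That the lists in 8.3 leave out non-deployment.* They are examples, and essential performance is defined in Instructions for Use that we do not have.
- *That such injuries would be rated not related.* Under 8.3 ii that rating needs evidence of a definite other cause, so this would be a guess.

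**Conclusion.** The concern holds for the ancillary device-performance endpoints and for the 6-of-6 rationale in 10.1. The 2.2 definition contradicts 10.1 and the protocol's prospective use of the term. With no independent label of fall type, correct deployments and non-injurious misses cannot be identified, and the discrimination result is either inverted (65%, 48% or 0% against a true 82%) or circular. These percentages rest on the laboratory sensitivity holding in the field and on the chosen values of p. Injurious misses, about 1.8 to 3.6 in 134 subjects with belts worn throughout, can be counted once the SAP specifies the linkage.

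The primary and secondary analyses do not use the belt's label and are unaffected. This should be corrected before analysis, but it does not threaten the main comparison.

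**What to change.** 1. **Definition.** Replace the 2.2 sentence with one based on fall mechanics, independent of injury and of the belt. Section 2.2 already contains a candidate: a fall from standing height with impact on the lateral or posterolateral hip.
2. **Classification.** Classify each fall from the site Fall report required by 8.3 iii, without sight of the belt label. Provide an indeterminate class for falls that nobody saw.
3. **Section 10.1.** State by what rule, and from what source, the six falls were called serious, and reconcile the count with the new definition. If the belt's label identified them, six deployments in six falls would follow largely by construction. The documents do not say.
4. **SAP.** Use all EMR falls in intervention subjects as the denominator. Cross-tabulate serious, non-serious and indeterminate falls by belt worn, airbag deployed and adjudicated major hip injury. Report deployments with no EMR fall per 1,000 wear-hours. List every non-deployment of a worn belt in a serious fall, with any resulting injury.

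The cost is wording in both documents and one item on the Fall report. EMR falls, deployments and wear are already collected and EDC-cloud matching is planned, but wear status must be derived at every fall and not only at primary events. The downside is that many unwitnessed falls may be indeterminate, and the reported sensitivity may be lower than one based on the cloud.
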